7.4 Suspected Adverse Reaction (SAR) and Adverse Reaction (AR)

Suspected adverse reactions (SARs) are the subset of all AEs for which there is a reasonable possibility to conclude that the study drug caused the event. For the purposes of IND safety reporting, 'reasonable possibility' means there is evidence to suggest a causal relationship between the study drug and the AE.

An "adverse reaction" (AR) is any AE caused by a drug. ARs are a subset of all SARs for which there is reason to conclude that the study drug caused the event.

An SAR implies a lesser degree of certainty about causality than an AR, which means any AE caused by a drug.

For reporting purposes, AEs assigned a relationship to study drug of "Probable," and "Possible" will be classified as SARs.

AEs assigned a relationship to study drug of "Unlikely" and "None" will not be classified as SARs.

7.5 Unexpected Adverse Events

The Investigator's Brochure (IB) provides Investigators with information (clinical and nonclinical) about the study drug. The IB includes those AEs for which a causal relationship is suspected or confirmed (SARs or ARs), as well as adverse events that may be predicted to occur based on the pharmacological properties of the drug. The IB is used as the basis for the Sponsor's determination of "unexpected" for reporting purposes.

"Unexpected" SARs are AEs not currently listed in the IB. An AE or SAR may also be considered "unexpected" if it is not listed in the IB at the specificity or severity that has been observed.

7.6 Withdrawal Due to Adverse Events

Withdrawal due to an AE should be distinguished from withdrawal due to insufficient response, according to the definition of AE noted earlier, and entered in the source records and EDC system.

When a subject withdraws due to an SAE, the SAE must be reported in accordance with the reporting requirements defined below.

7.7 Serious Adverse Events

7.7.1 Definition of Serious Adverse Events

Serious adverse events (SAEs) are defined as those AEs that meet any of the following criteria:

- Life threatening, that is, any event that, in the opinion of the Investigator, poses an immediate risk of death from that event
- Results in death
- Results in or prolongs hospitalization
- Results in persistent or significant incapacity or substantial disruption of the ability to conduct normal life functions
- Results in congenital anomaly/birth defect

- Is an important medical event that may require an intervention to prevent one of the outcomes listed above
- For clarification, an AE or suspected adverse reaction (SAR) is “life-threatening”, if, in the view of the Investigator or the Sponsor, its occurrence places the subject at immediate risk of death. It does not include an AE or SAR that, had it occurred in a more severe form, might have caused death

The Investigator should exercise medical and scientific judgment when deciding whether SAE reporting is appropriate in other situations not strictly meeting the listed criteria above. Examples of important medical events which may meet the definition of an SAE include: intensive treatment in an emergency room or at home for allergic bronchospasm, certain laboratory abnormalities (e.g., blood dyscrasias), convulsions that do not result in hospitalizations, or development of drug dependency or drug abuse.

Pre-planned hospitalizations and/or elective surgical procedures may not be considered SAEs.

Hospitalization does not include the following:

- Rehabilitation facilities;
- Hospice facilities;
- Respite care (e.g., caregiver relief);
- Skilled nursing facilities;
- Nursing homes;
- Routine emergency room admissions;
- Scheduled or elective same day surgeries (as outpatient/same day/ambulatory procedures).

Hospitalization or prolongation of hospitalization in the absence of a precipitating, clinical adverse event is not in itself an SAE. Examples include:

- Admission for treatment of a pre-existing condition not associated with the development of a new AE or with a worsening of the pre-existing condition (e.g., for work-up of persistent pre-treatment lab abnormality);
- Social admission (e.g., subject has no place to sleep);
- Administrative admission (e.g., for yearly physical exam);
- Optional admission not associated with a precipitating clinical adverse event (e.g., for elective cosmetic surgery);
- Pre-planned treatments or surgical procedures should be noted in the baseline documentation for the entire protocol and/or for the individual subject.

Diagnostic and therapeutic non-invasive procedures, such as surgery, should not be reported as AEs. However, the medical condition for which the procedure was performed should be reported, if it meets the definition of an AE. For example, an acute appendicitis that begins during the AE reporting period should be reported as an AE and the resulting appendectomy should be recorded as treatment of the AE.

The Investigator should contact the Sponsor's Medical Monitor immediately if there is a question as to whether or not an AE meets the criteria for serious.

7.8 Procedures for Reporting and Recording Serious Adverse Events & Suspected Serious Adverse Reactions

All SAEs, irrespective of relationship to study treatment, must be reported to the Sponsor and the Medical Monitor as soon as possible, but no later than 24 hours from the time of notification. All AE/SAE information and appropriate supporting documentation must be sent electronically to the Medical Monitor & Sponsor.

Medical Monitor:

[name], DMD, MD, RAC

[contact]

Email: [contact]

Urgent safety issues should be discussed by telephone with the Medical Monitor as soon as the Investigator or members of the study staff become aware of the issue.

It is very important that the SAEs be reported as soon as possible via the EDC and the information be filled out as completely as possible at the time of the initial report. This includes the Investigator's assessment of causality. A brief description of the event must be provided at the time of the initial report. After the initial SAE report has been submitted, relevant follow-up information should be submitted as soon as possible, preferably within one (1) business day of receipt. If the follow-up information changes the Investigator's assessment of causality, this should also be added as follow-up information in the EDC system.

Additional SAE-related supporting documents, such as copies of hospital reports, lab reports, discharge summaries, and autopsy reports, if applicable, may be requested. All subject identifiers, except the subject's initials and unique study identification number, must be removed from documents prior to submission to the Medical Monitor and other Sponsor designees. Subjects' names, personal identification numbers (i.e., medical record numbers), and addresses, etc., should be removed or blocked-out.

Reporting of a suspected serious adverse reaction (SUSAR) should not be delayed in order to obtain additional information. Any additional information, if collected, can be reported as a follow-up to the initial report. Any SAE that occurs at any time during the study, whether or not related to study drug, must be reported to the Medical Monitor within 24 hours of first awareness at the site.

The Investigator is responsible for the information recorded on SAE reports. It is the Investigator's responsibility to ensure that the SAE information in the EDC system and source documents are accurate, consistent and in agreement. The Investigator is responsible for continuing SAE follow-up. The results of any additional assessments of the SAE must be reported to the Medical Monitor as an update to the SAE as soon as possible, but no later than 24 hours after first awareness. Details on the SAE reporting procedure are provided in the SAE Reporting Guidelines. Criteria for determining severity and the relationship to study drug for the updated SAE will be the same as those previously described in Sections 7.2 and 7.3.

7.8.1 Reporting Serious Adverse Events to the FDA and IRB

The Investigator will comply with the applicable regulatory requirements related to the reporting of SAEs to the IRB. The completed SAE report will be used by the Sponsor in regulatory filings and may be used by the Investigator to convey SAE information to the IRB.

7.8.2 Following Adverse Events and Serious Adverse Events

All AEs should be followed in accordance with good medical practice until resolution or the adverse event or condition has stabilized. AEs will be followed for one week post last dose in all Study Arms. All SAEs will be followed until the outcome is known or the subject's condition has stabilized.

7.9 Pregnancy

A negative urine pregnancy test result must be confirmed at Screening and Baseline visits.

Female subjects of childbearing potential must agree to use one of the following forms of contraception from screening through the last study visit: hormonal (oral, implant, or injection) begun >30 days prior to screening; barrier (condom, diaphragm, or cervical cap with spermicide); intrauterine device (IUD). Acceptable contraceptive options may also include; abstinence, monogamous relationship with same sex partner or partner who has had a vasectomy at least six (6) months prior to the screening visit. In the unlikely event a subject becomes pregnant during the study, the subject will be withdrawn from the study immediately upon confirmation of pregnancy. These subjects will be required to return to the study center to undergo early termination procedures (Sections 9.3.2 and 9.3.3).

In addition, any documented pregnancy will be tracked and followed through outcome. While pregnancy itself is not considered an AE or an SAE, any pregnancy complications or elective termination of a pregnancy for medical reasons will be recorded as an AE and evaluated as a possible SAE.

All pregnancies are to be reported immediately to the Medical Monitor.

7.10 Management of Medical Emergency (Hypersensitivity)

If a hypersensitivity reaction occurs during the administration of study drug, the Investigator will discontinue the administration of study drug and provide general supportive measures. If an adverse event occurs after administration of study drug, the Investigator will provide general supportive measures.

7.11 Management of Dosing Error

If a dosing error does occur, the Investigator will; 1) monitor the subject, 2) provide general supportive measures, as needed, 3) notify the Medical Monitor and the Sponsor within 24 hours, and, 4) report the dosing error to the IRB, per site's policy.

8. STATISTICAL CONSIDERATIONS

8.1 General Considerations

Protocol C3J16-V204-00 is a phase 2, single-blind, randomized, placebo controlled study designed to evaluate the safety and microbiological activity of C16G2 Varnish applied directly to the tooth surface. Study subjects will receive a single C16G2 Varnish or Placebo administration on six separate days. The study will evaluate 27.2 mg and potentially 13.6 mg and/or 54.4 mg C16G2 Varnish or Placebo administrations.

The objectives of the study are to evaluate the safety of multiple C16G2 Varnish or Placebo administration in subjects 12-75 years of age, to assess the targeted antimicrobial activity of C16G2 Varnish or Placebo as measured by a reduction in the number of *Streptococcus mutans* in saliva and dental plaque, and to assess total bacteria in stimulated saliva and dental plaque.

For the summary table presentations, data will be summarized in tabular format by treatment group. All statistical analysis will be descriptive in nature. Descriptive summary statistics will include N, mean, standard deviation, median, range (minimum and maximum) for continuous variables, and frequency counts and percent for categorical variables.

8.2 Randomization

The study will enroll subjects into up to three study arms. Up to 33 subjects will receive multiple doses of study drug (27.2 mg and 13.6 mg or 54.4 mg C16G2 Varnish or Placebo) applied with a small brush typically used in dental varnish administration (for details see Appendix A). Subjects will be enrolled in 8:3 ratio. A microbiology review will be conducted after all subjects in Arm 1 have completed Visit 8 (Day 14) and a determination will be made whether to enroll additional 11 subjects into Study Arms 2 and/or 3 (13.6 mg and/or 54.4 mg C16G2 Varnish or Placebo).

After confirmation of study eligibility, subjects will be randomized at Visit 3 (Day 0) by authorized study staff according to the master randomization schedule from the Sponsor's study statistician. The randomization schedule and associated documentation will be kept in a secure location.

8.3 Blinding

The study will be conducted in a single-blind, placebo-controlled manner. All study subjects will be blinded to the treatment assignment, while the Investigator, study staff/clinicians and the Sponsor's assigned team members (e.g., the Clinical Monitor and the Medical Monitor) will be unblinded as to whether subjects are receiving C16G2 or Placebo.

Study drug (C16G2 Varnish or Placebo) will be packaged identically to ensure blinding.

8.4 Sample Size Determination

The total number of subjects planned for this study is up to 33. There are no data on which to base formal sample size calculations for this study. The data generated in this study will assist with ongoing clinical development of C16G2 Varnish. Subjects' data in this study will provide information on the safety and microbiology of multiple administrations of C16G2 Varnish or Placebo. Subjects may be replaced at the Sponsor's discretion.

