Microbiology assessments did not demonstrate an apparent reduction or increase in *S. mutans* and other bacterial species outside of the variation observed in the placebo cohort, indicating that single C16G2 doses formulated as a mouth rinse did not impact the oral microbiome.

Study C3J16-V102-00, a Phase 1, single-blind, randomized, placebo-controlled, dose-escalation study evaluated the safety and efficacy of single 13.6 mg, 27.2 mg, 54.4 mg C16G2 Varnish or Placebo administrations.

The objectives of this study were to evaluate the safety and microbiology of C16G2 Varnish formulation in healthy adult subjects and to assess the targeted antimicrobial activity of C16G2 as measured by a reduction in the number of salivary *S. mutans*. In addition, the study assessed the bacterial composition in the oral cavity over 28 days post single study drug administration in healthy adult dental subjects.

A total of 48 adult healthy subjects were enrolled, of which 30 subjects received C16G2 and 18 subjects received placebo. C16G2 was well-tolerated with no deaths and no other serious or severe AEs. No study drug-related treatment-emergent AEs were reported and no subject was discontinued due to an AE. No clinically significant changes in vital signs were observed in association with the administration of C16G2. Oral cavity assessments and targeted physical exams did not indicate any clinically relevant changes due to study drug administration. Microbiology evaluations demonstrated a significant decrease in *S. mutans* levels in saliva and plaque samples in each dose level. The 27.2 mg dose group showed the greatest decrease in *S. mutans* compared to Placebo and the other two dose groups. Total bacteria levels did not change significantly post study drug administration. The clinical study report for this study is currently in preparation.

1.1.2 Phase 2

To enhance the targeted *S. mutans* killing activity of C16G2 in dental plaque, C3 Jian formulated the drug product for both mouth rinse and gel application. C3J13-201-01, a double-blind, placebo-

controlled study, evaluated different combinations of multiple C16G2 Gel and/or C16G2 mouth rinse administrations at two dose levels. To determine the most effective mode of gel application, gel was applied by manual toothbrush, Sonicare™ toothbrush and upper and lower custom dental trays.

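### The no-data statement in Section 8.4 is too broad given the single-dose varnish study, and the small descriptive cohorts should be reported with placebo differences and confidence intervals

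*Combined protocol and SAP*

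**What the plan says.** On sample size, Section 8.4 says "The total number of subjects planned for this study is up to 33" and then "There are no data on which to base formal sample size calculations for this study". The synopsis (Statistical Methods, Sample Size) makes the same no-data statement. Section 8.2 adds "Subjects will be enrolled in 8:3 ratio", and the Section 5 table shows 8 active and 3 placebo subjects at each of three strengths.

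On earlier varnish data, Section 1.1.1 describes Study C3J16-V102-00, which "evaluated the safety and efficacy of single 13.6 mg, 27.2 mg, 54.4 mg C16G2 Varnish or Placebo administrations". It reports: "A total of 48 adult healthy subjects were enrolled, of which 30 subjects received C16G2 and 18 subjects received placebo". On results it says "Microbiology evaluations demonstrated a significant decrease in *S. mutans* levels in saliva and plaque samples in each dose level", and "The 27.2 mg dose group showed the greatest decrease in" *S. mutans* compared with placebo and the other two dose groups. Section 1.3 carries this ranking into the dose rationale, and Section 1.6 cites the study's adverse events.

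On analysis, Section 8.1 says "All statistical analysis will be descriptive in nature" and lists N, mean, SD, median and range, or counts and percentages. Section 8.7.6.5 plans these summaries for the microbiology by time point and treatment group, compared with Baseline, and leaves further microbiology detail to a SAP. Section 8.7.6.1 plans adverse event incidence and duration by group. No section mentions a confidence interval or an active-minus-placebo estimate, or says whether placebo subjects are pooled across cohorts.

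On use of the data, Sections 3.1.1 and 8.2 and the synopsis have microbiology results reviewed to decide whether the 13.6 mg and/or 54.4 mg cohorts are enrolled. The synopsis and Section 3.1.1 call this review unblinded and ongoing; Section 8.2 places it after all Arm 1 subjects have completed Visit 8.

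**The concern.** Two things sit badly together. The protocol relies on results from the same dosage form, strengths and endpoint when it discusses dose, but says that nothing is available when it discusses sample size. A reader of Section 8.4 alone would not learn that a single-dose estimate of variability might exist.

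The second matters more. The Arm 1 review looks at 8 active and 3 placebo subjects, and the only planned comparison is with Baseline. All subjects have a professional prophylaxis 2 to 7 days before dosing, use the supplied fluoride toothpaste and floss, brush and floss in clinic before each application, and have a vehicle applied to the teeth. A change from Baseline in the active group therefore mixes any drug effect with whatever these do. The placebo subjects are there to separate the two, but the plan never forms that contrast or shows how imprecise it is. Likewise, a bare count of no events in a small group does not show how high a rate it leaves open. That bears on safety, the primary objective.

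**Working it through.** **The plan's own figure.** Three cohorts of 8 + 3 give 3 × 11 = 33, which agrees with Section 8.4. No alpha, power, effect size, SD or precision target is stated, so there is no calculation to reproduce.

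**Side by side on data availability.** The single-dose study shares with this trial the dosage form, the strengths (13.6, 27.2, 54.4 mg), a placebo group, and *S. mutans* in saliva and plaque. It differs in giving one application and in enrolling adults only; this trial gives repeated applications at ages 12 to 75. It can therefore offer a starting value for variability but not the multiple-dose effect. If all 48 subjects were evaluable in four groups, a pooled SD would have 48 − 4 = 44 df, and its 95% CI would run from about 0.83 to 1.26 times the estimate. That is adequate for stating a precision. The documents do not print that SD.

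**Precision of active minus placebo** (difference in mean log10 change from Baseline, common SD, t-based).

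Half-width = t(0.975, n1 + n2 − 2) × SD × √(1/n1 + 1/n2)

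- 8 v 3, as at the Arm 1 review: 2.262 × √(1/8 + 1/3) = 2.262 × 0.677 = 1.53 SD.
- 8 v 9, one strength against placebo pooled over three cohorts: 2.131 × √(1/8 + 1/9) = 2.131 × 0.486 = 1.04 SD.

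The second figure applies only at the end and only if all three cohorts enrol. The SD of log10 change has to be assumed:

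| Assumed SD (log10) | 8 v 3 | 8 v 9 |
|---|---|---|
| 0.5 | ±0.77 | ±0.52 |
| 1.0 | ±1.53 | ±1.04 |

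**Adverse event proportions with no events** (exact two-sided 95% upper limit).

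Upper limit = 1 − 0.025^(1/n)

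- 0 of 8: 1 − 0.025^(1/8) = 0.369, or 37%.
- 0 of 24 (all active subjects): 1 − 0.025^(1/24) = 0.142, or 14%.

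These limits need no assumed SD.

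**The case against.** The case for leaving the plan alone is substantial.

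- **The sentence can be read narrowly.** It refers to this study, and Section 8.4 goes on to describe the information sought as concerning multiple administrations. Section 1.3 says that repeated dosing may alter the effect. A reader might infer that the justification is simply false. The documents do not support that: the wording is too wide, but a narrower statement would be sound. Nor do they show that the sponsor holds a usable SD or that the product was identical. The earlier study's report was still in preparation, no mean or SD is printed, and Section 5.1.2 names two vehicles without saying which the earlier study used.
- **The planned comparison is with Baseline.** For one active group of 8, the half-width is 2.365/√8 = 0.84 SD, or ±0.42 to ±0.84 log10 over the same assumed range, much tighter than 1.53 SD. This is correct for change from Baseline, but that quantity does not isolate the drug.
- **No formal calculation is required.** The primary objective is safety and the analysis is descriptive. This stands.
- **Intervals might appear elsewhere.** Section 8.7.6.5 defers microbiology detail to a SAP, and the document supplied contains no separate SAP text. That leaves the microbiology part open, but the deferral does not cover adverse events. N, SD and counts would also let a reader derive the intervals, though the plan does not ask for it.
- **No safety conclusion rests on 8 subjects.** The synopsis evaluates safety on up to 33 subjects, and the decision on further arms rests on microbiology. This stands: the 37% figure shows what a bare count leaves out and does not describe a conclusion the plan draws.

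**Conclusion.** The point holds as a minor one. The no-data sentence is broader than the protocol's own account allows and needs narrowing; by itself that changes no result. The gain lies in the reporting. With 8 v 3 the placebo difference is known only to within 1.53 SD, and with 8 v 9 to within 1.04 SD. No events in 8 or in 24 leave true rates up to 37% or 14% open. Showing these figures changes what the small cohorts can be said to demonstrate.

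The SD multiples assume a common SD and approximately normal log10 changes. The log10 half-widths also depend on the assumed SD of 0.5 to 1.0, which has no source in the documents.

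Two stronger readings should be avoided. One is that an effect of about 1 log10, as in the rinse and gel studies, would be lost in the noise here. Section 1.3 gives that figure as suppression during dosing with other formulations, not as a difference from placebo, so it should not be set against the between-group half-width. The other is that more subjects are needed. The plan sets no target difference, power or precision, so no larger number follows.

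**What to change.** 1. In Section 8.4 and the synopsis, narrow the sentence to say that no data exist on multiple varnish administrations. Cite the SD of log10 change from Study C3J16-V102-00, if available, as a single-dose starting value, and give the resulting half-widths. Changing only one of the two places would create a new inconsistency.
2. In Section 8.7, have the microbiology tables, including those used for the Arm 1 review, report the active-minus-placebo difference in log10 CFU change from Baseline with a 95% CI. State whether and when placebo is pooled across cohorts.
3. In Section 8.7, attach exact 95% CIs to the treatment-emergent adverse event proportions.

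The cost is a short text edit in two places, a few table columns, and intervals that will look wide. The number of subjects and the conduct of the trial do not change. Intervals do not supply a criterion for opening further arms; they show the reviewers how much the 8 v 3 comparison can bear.
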